#### **7.5.2.8 Overall Survival (OS)**

OS is defined as the time from the start of study treatment to date of death due to any cause. In the absence of death, survival time will be censored at the last date the patient is known to be alive (i.e., date of last contact). Patients lacking data after their first dose of study drug will have their survival time censored at Day 1.

OS will be analyzed by cohort using Kaplan-Meier methodology and Kaplan-Meier plots will be provided. The median OS and its 2-sided 95% CI will be calculated as appropriate. The OS rates at 6 and 12 months, and every 6 months thereafter, will be reported and their 2-sided 95% CIs will be calculated.

## 7.6 Safety Analyses

All safety analyses will be performed by cohort and total using the safety analysis set.

Adverse events will be coded using Medical Dictionary for Regulatory Activities (MedDRA, Version 19.1 or higher).

Laboratory values will be graded according to the National Cancer Institute (NCI) Common Terminology Criteria for Adverse Events (CTCAE version 5.0 or higher).

Concomitant medications will be coded using WHO Drug (version: June 2016 or more recent).

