3.1.1 Dose-Limiting Toxicity

DLTs will be assessed during the safety run-in portion of the study. Patients will be replaced for DLT evaluation if they do not complete the DLT evaluation period and do not experience a DLT before they discontinue from the study or start subsequent cancer therapy.

The DLT evaluation period for each safety run-in patient is defined as 28 days after the first dose of tisotumab vedotin. Patients who experience DLTs should not receive further treatment with tisotumab vedotin, unless clinical benefit is demonstrated with adequately managed toxicity. Subsequent treatment with tisotumab vedotin will be defined by the medical monitor in discussion with the site investigator in the context of the type of AE observed.

The IB for tisotumab vedotin describes AEs commonly observed, as well as less common serious findings. The IB should be referenced when attributing causality; however, the final decision regarding causality is at the discretion of the investigator.

A DLT is defined as:

One of the following that is observed within **28 days** of the first dose of tisotumab vedotin and is considered related to the drug:

- Grade 4 neutropenia (i.e., ANC $<0.5 \cdot 10^9$ cells/L) for minimal duration of seven days.
- Grade 3 and 4 febrile neutropenia (i.e., ANC $<1.0 \cdot 10^9$ cells/L with a single temperature of $>38.3^{\circ}\text{C}$ or a sustained temperature of $\geq 38^{\circ}\text{C}$ for more than one hour).
- Grade 4 thrombocytopenia ($\leq 25.0 \cdot 10^9$ platelets/L).
- Grade 3 thrombocytopenia associated with bleeding episodes.
- Grade 3 or higher ocular adverse events
- Major bleeding, defined as:
 - Fatal bleeding
 - Symptomatic bleeding in a critical area organ, such as intracranial, intraocular, retroperitoneal, intra-articular or pericardial, or intramuscular with compartment syndrome
 - Bleeding causing a drop in hemoglobin level of 20 g/L (1.24 mmol/L) or more
 - Bleeding leading to transfusion of two or more units of whole blood or red cells.
- Stevens Johnson syndrome, toxic epidermal necrolysis, Grade ≥ 3 cutaneous vasculitis.
- Grade 3 neuropathy (not improving to Grade 1 within 3 weeks following end of treatment) and Grade 4 neuropathy.
- Grade 3 infusion -related AEs that do not resolve to Grade 1 or baseline within 24 hours.
- Grade 4 infusion -related events including anaphylaxis.

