9.3.1.7 Analysis Sets

The full analysis set (FAS) includes all patients who received any amount of study drug. All efficacy analyses will be based on the FAS.

The safety analysis set includes all patients who received any amount of study drug, and thus is equivalent to the FAS. All safety analyses will be based on the safety analysis set.

The DLT evaluable analysis set includes all patients who received any amount of study drug and have completed the DLT evaluation period or have experienced a DLT. The DLT evaluable set applies only to the safety run-in cohort.

The efficacy-evaluable (EE) analysis set includes patients who received any amount of study drug and had at least one post-baseline disease assessment per RECIST v1.1 or discontinued from the study or started subsequent cancer therapy. The EE analysis set will be used for supplemental analysis of efficacy endpoints as applicable.

The CA-125 evaluable analysis set includes patients with ovarian cancer who have an elevated baseline CA-125 value of $\geq 2 \times$ ULN and within 2 weeks prior to the first dose of study drug. The CA-125 evaluable analysis set will be used for the analysis of CA-125 response rate.

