9.3.8 Safety Analyses

All safety analyses will be performed using the safety analysis set.

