## **3 STUDY ENDPOINTS**

### **3.1 Primary Endpoint**

For the safety run-in, the primary endpoint is the incidence of dose limiting toxicities (DLTs) or other unacceptable toxicities. For Parts A and B, the primary endpoint is confirmed objective response rate (ORR) (confirmed complete response [CR] and confirmed partial response [PR] per RECIST v1.1) as determined by the investigator.

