## **4 STUDY DESIGN**

This is an open-label, phase 2 study with an initial safety run-in period. The safety run-in period will evaluate the safety of a dose-dense schedule and will start at a 0.9 mg/kg dose level. If 0.9 mg/kg is considered safe and tolerable, the dose level will be escalated to 1.2 mg/kg. Otherwise it will be de-escalated to 0.65 mg/kg. Each dose level will enroll approximately 6 patients. Patients who do not complete the DLT period will be replaced.

A dose level is considered safe and tolerable if no more than 1 patient experiences a DLT among 6 patients during the DLT period. The highest dose level that is considered safe will be the recommended phase 2 dose (RP2D) and will be used in Part A. If no RP2D for the dose-dense schedule is identified, Part A will be a single arm of the Q3W regimen and Part B will not enroll.

In Part A, 60 patients will be randomized in a 1:1 ratio to receive tisotumab vedotin 2.0 mg/kg intravenously (IV) every 3 weeks (Q3W regimen) or the safety run-in RP2D on Days 1, 8, and 15 of every 4-week cycle (dose-dense regimen; 3Q4W) if a RP2D has been identified. Randomization will be stratified by first line vs. second line PROC and histology (serous vs. non-serous).

Based upon antitumor activity and safety data, one Part A treatment arm may be expanded to enroll up to an additional 70 patients to further characterize safety and antitumor activity of tisotumab vedotin for patients with PROC. The analysis to support expansion will be conducted when approximately 30 patients per arm have at least one post-baseline response assessment per RECIST v1.1 or have discontinued from the study or started subsequent cancer therapy.

Part B will enroll approximately 80 patients with PROC including approximately 60 patients who have received 1 to 3 prior lines of therapy, including bevacizumab treatment. Part B will further characterize the long-term efficacy, safety, and PK assessments of 0.9 mg/kg tisotumab vedotin on Days 1, 8, and 15 of every 4-week cycle (dose-dense regimen) if the 0.9 mg/kg dose level is considered safe and tolerable in the safety run-in period. Enrollment in this cohort may discontinue when Part A begins enrollment.

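### The SAP leaves out the protocol's DLT-evaluable set, so run-in DLT incidence is computed on all dosed patients; it also assigns ATA incidence to two different sets

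*SAP*

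**What the plan says.** **DLT.** SAP 3.1 sets the run-in endpoint: "For the safety run-in, the primary endpoint is the incidence of dose limiting toxicities (DLTs) or other unacceptable toxicities". Protocol 9.3.1.7 defines a set for evaluating it, made up of dosed patients who "have completed the DLT evaluation period or have experienced a DLT", and adds: "The DLT evaluable set applies only to the safety run-in cohort". SAP Section 5 lists six sets (full analysis, safety, PK, ATA-evaluable, efficacy-evaluable and CA-125-evaluable), and the DLT-evaluable set is not among them. SAP 7.6 says: "All safety analyses will be performed by cohort and total using the safety analysis set". SAP 5.2 makes the safety set everyone given any drug, and SAP 7.6.1 includes DLTs in the adverse event summaries without naming another set.

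Both documents foresee dosed patients who are not evaluable. Protocol 3.1.1: "Patients will be replaced for DLT evaluation if they do not complete the DLT evaluation period and do not experience a DLT". SAP Section 4: "Patients who do not complete the DLT period will be replaced". The dose rule, also in SAP Section 4, is: "A dose level is considered safe and tolerable if no more than 1 patient experiences a DLT among 6 patients during the DLT period".

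SAP 9.1 declares no change from the protocol, and SAP 9.2 says the SAP was updated to align with Amendment 4.

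**ATA.** SAP 5.4 defines an ATA-evaluable set (baseline status plus at least one post-treatment sample) and bases ATA analyses on it. SAP 7.7.2 summarises ATA incidence on the safety set, as protocol 9.3.5 does.

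**PRO.** SAP 2.3 and protocol 9.3.7 limit patient-reported outcomes to US patients in Parts A and B. SAP 7.7.4 defines the completion rate over the FAS and does not repeat that limit.

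**The concern.** A patient who stops before the end of the 28-day window without a DLT has not been observed long enough to count as DLT-free. The protocol's set excludes such a patient; the SAP's only available denominator includes her. Every replaced patient therefore dilutes the DLT incidence, always in the direction that makes the dose level look better tolerated.

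For ATA, two programmers could each follow the SAP and report different rates for a listed secondary endpoint. The direction of the difference is not known in advance. It depends on whether the patients lacking a baseline or post-treatment result are counted as negative or as positive on the safety set.

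For PRO, 7.7.4 read on its own counts patients who were never given a questionnaire as non-completers, so completion would look worse than it was.

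**Working it through.** The plan gives no figure to reproduce here. The check compares the sections and then sizes each denominator effect. Every count marked as assumed is absent from the documents.

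**1. DLT incidence**

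The SAP leads to the all-dosed denominator as follows:

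- Section 5 contains no DLT-evaluable set.
- Section 7.6 assigns all safety analyses to the safety set.
- Section 7.6.1 places DLTs among those analyses and makes no exception.
- Section 4 allows replacement, so dosed patients can outnumber evaluable ones.

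Let d be the patients with a DLT, 6 the evaluable patients at a dose level, and r the replaced patients without a DLT (assumed 0, 1 or 2). The evaluable rate is d/6 and the SAP's rate is d/(6 + r). The intervals are Clopper-Pearson 95%: for n patients, the lower limit is the 0.025 quantile of Beta(d, n − d + 1) and the upper limit is the 0.975 quantile of Beta(d + 1, n − d). When d = 0 the lower limit is 0 and the upper limit is 1 − 0.025^(1/n).

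| DLTs | r = 0 (same as evaluable) | r = 1 | r = 2 |
|---|---|---|---|
| 0 | 0/6 = 0% (0–45.9%) | 0/7 = 0% (0–41.0%) | 0/8 = 0% (0–36.9%) |
| 1 | 1/6 = 16.7% (0.4–64.1%) | 1/7 = 14.3% (0.4–57.9%) | 1/8 = 12.5% (0.3–52.7%) |
| 2 | 2/6 = 33.3% (4.3–77.7%) | 2/7 = 28.6% (3.7–71.0%) | 2/8 = 25.0% (3.2–65.1%) |

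On the evaluable set the first column applies whatever r is. With no DLTs the point estimate does not move, but the upper limit still falls.

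**2. ATA incidence**

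SAP 7.7.2 specifies only one ATA analysis, the incidence rate. SAP 5.4 therefore cannot be read as referring to some other ATA analysis, and the two sections conflict.

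To show the mechanism, assume 80 treated patients (the planned size of Part B) and 6 positives, which gives 6/80 = 7.5% on the safety set. Let u be the negatives who are not evaluable (assumed 0 to 16) and b the positives without a baseline (assumed 0 to 2). The evaluable-set rate is (6 − b)/(80 − u − b).

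- Lowest, u = 0 and b = 2: 4/78 = 5.1%.
- Highest, u = 16 and b = 0: 6/64 = 9.4%.

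The range depends on these inputs. With 4 positives, all of them evaluable, and 80 to 100% of the 80 patients evaluable, the safety-set rate is 4/80 = 5.0% and the evaluable-set rate runs from 4/80 = 5.0% to 4/64 = 6.25%.

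**3. PRO completion**

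If only US patients receive the forms, the highest possible completion rate over a cohort's FAS is US patients divided by the cohort FAS, which is the US share. If 50 to 75% of a cohort is from the US (assumed), completion cannot exceed 50 to 75% even if every US patient answers. SAP 6.1 summarises the run-in separately, so run-in patients are not added to this denominator.

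**The case against.** The strongest objection is that the SAP contradicts no explicit protocol instruction on DLTs. Protocol 9.3.8 itself says "All safety analyses will be performed using the safety analysis set", 9.3.1.7 says much the same, and nothing in the protocol assigns an analysis to the DLT-evaluable set. This is correct, and the point is therefore an omission and not an override. It does not remove the problem. A set defined only for the run-in, by completion of the DLT window, has no evident use other than DLT evaluation, and protocol 9.3 leaves the fuller analysis plan to the SAP.

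A second objection is that little depends on the difference. The dose rule has its own denominator of 6, every DLT is listed, the two rates agree if nobody is replaced, and the exact intervals overlap widely. All of this stands, and it limits the point to how the endpoint is reported.

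A third is that moving only DLTs to the evaluable set gives one primary endpoint two denominators, since a replaced patient can have another unacceptable toxicity. That is a fair caution. The two components can be reported separately, each on its own stated set, which avoids the difficulty.

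On ATA, 7.7.2 is the more specific section and agrees with the protocol, so 5.4 is the outlier and the conflict is easy to settle. The conflict is nonetheless real, and the rates above illustrate it without measuring it. On PRO, the US limit appears elsewhere in the SAP, and the compliance rate in 7.7.4 already uses patients expected to respond, so this part is editorial.

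**Conclusion.** The concern holds. Followed as written, the SAP computes the DLT part of the run-in primary endpoint on all dosed patients, which can only leave the rate unchanged or lower it. With 6 evaluable patients and up to two replaced, the reduction is at most 4.2 percentage points for 1 DLT (16.7% to 12.5%) and 8.3 points for 2 DLTs (33.3% to 25.0%). The replacement count is an assumption, and with none there is no effect. This is a reporting bias and does not change a dose decision.

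The ATA conflict is a direct contradiction within the SAP about a secondary endpoint. Its size and direction cannot be known from the documents. The PRO point is minor and concerns a data-quality descriptor, not an endpoint.

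These points should be corrected before database lock, because a later choice of denominator would be made with the data in view.

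**What to change.** - **DLT.** Add the protocol's DLT-evaluable set to SAP Section 5 and name it in 7.6.1 for run-in DLT incidence. Keep other unacceptable toxicities and all remaining safety summaries on the safety set, and report the two components of the endpoint separately.
- **ATA.** Name the same primary set in SAP 5.4 and 7.7.2. The repair consistent with the protocol is to correct 5.4 to the safety set. If the team prefers the evaluable set, because developing ATA can only be judged with a baseline and a post-treatment result, change 7.7.2 and record the departure from the protocol in SAP Section 9. Give the other set as supportive.
- **PRO.** In SAP 7.7.4, define the completion denominator as US patients in the FAS of Parts A and B.

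The cost is a few lines of SAP text and small programming changes. Site conduct is unaffected, so under protocol 9.3 no amendment is needed. The reported DLT rate may rise slightly or stay the same. The ATA rate could move either way if the evaluable set is chosen.

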### 7.6.1 Adverse Events

AEs will be summarized by MedDRA preferred term in descending frequency of occurrence unless otherwise specified. For incidence reporting, if a patient reports more than one AE that was coded to the same system organ class or preferred term, the patient will be counted only once for that specific system organ class or preferred term.

Treatment-emergent AE (TEAE) is defined as a newly occurring or worsening AE after the first dose of study treatment and with onset date on or before 30 days after the last dose of study drug. See Appendix B for details regarding treatment-emergent classification.

Summaries of AEs will be provided by cohort and total for the following:

- TEAEs
- Grade 3 or higher TEAEs
- DLTs
- TEAEs by system organ class and preferred term
- TEAEs by system organ class, preferred term, and maximum severity. At each system organ class or preferred term, multiple occurrences of events within a patient are counted only once at the highest severity
- TEAEs related to tisotumab vedotin
- TEAEs leading to dose delay
- TEAEs leading to dose reduction
- TEAEs leading to dose elimination
- TEAEs leading to unplanned dose adjustment
- TEAEs leading to treatment discontinuation
- TEAEs leading to death
- Infusion related reactions

- Treatment-emergent SAEs
- Treatment-emergent SAEs by system organ class and preferred term
- Treatment-emergent SAEs related to tisotumab vedotin
- Treatment-emergent Adverse Events of Special Interest (AESI) by system organ class, preferred term and maximum severity
- Treatment-emergent AESI
- Serious AESI

All TEAEs, Treatment-emergent SAEs, TEAEs leading to treatment discontinuation, TEAEs leading to death, and DLTs will be listed.

#### **7.6.1.1 Adverse Events of Special Interest**

Adverse events of ocular AEs, peripheral neuropathy, and bleeding are considered AESI. The search criteria for AESI will be maintained in a separate document and will be finalized prior to database lock. Shift tables comparing the highest post-baseline to baseline CTCAE grade will be presented when applicable.

Time to onset will be summarized for subjects who have the events that meet certain search criteria. Time to onset is defined as time (days) from the date of first dose to the start date of first event (start date of first event – date of first dose + 1).

Time to resolution will be summarized for events that meet certain search criteria and have the outcome of ‘recovered/resolved’ or ‘recovered/resolved with sequelae’. Time to resolution is defined as time (days) from the start date of the event to the end date of the same event (end date of the event – start date of the event + 1).

For events that are not resolved, improvement is defined as a decrease by at least one grade from the worst grade as of the latest assessment. For events that meet the definition of ‘improvement’, time to improvement will be calculated as time from the worst grade of the event to the date the event is improved.

Time to onset, resolution and improvement will be summarized by descriptive statistics (mean, standard deviation, median, minimum, and maximum). Time to onset will be summarized at the subject level. Time to resolution and improvement will be summarized at the event level.

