3. No other immediately apparent possible causes of aminotransferase elevation and hyperbilirubinemia, including, but not limited to, viral hepatitis, pre-existing chronic or acute liver disease, or the administration of other drug(s) known to be hepatotoxic.

Reporting Requirements

Any potential Hy's Law case should be handled as a suspected unexpected serious adverse reaction (SUSAR) associated with the use of the drug and reported promptly to the sponsor.

Reporting should include all available information and should initiate close follow-up until complete resolution of the problem and completion of all attempts to obtain supplementary data.

Follow-up for Abnormal Laboratory Results Suggesting Potential DILI

In general, an increase of serum ALT or AST to $>3 \times$ ULN should be followed by repeat testing within 48 to 72 hours of serum ALT, AST, alkaline phosphatase, and total bilirubin, to confirm the abnormalities and to determine whether they are worsening.

Appropriate medical assessment should be initiated to investigate potential confounding factors and alternative causes of hepatotoxicity.

7.7.8.3 Reporting Periods for Adverse Events, Serious Adverse Events, and Adverse Events of Special Interest

The safety reporting period for all AEs and SAEs is from study Day 1 (predose) through the EOT visit or 30 days after the last study treatment (tisotumab vedotin), whichever is later.

However, all study protocol-related AEs are to be recorded from the time of informed consent. All SAEs that occur after the safety reporting period and are considered study treatment-related in the opinion of the investigator should also be reported to the sponsor.

SAEs will be followed until significant changes return to baseline, the event stabilizes (recovering/resolving) or is no longer considered clinically significant by the investigator, or the patient dies or withdraws consent. All non-serious AEs will be followed through the safety reporting period. Certain non-serious AEs of interest (i.e., all ocular events) will be followed until resolution, return to baseline, or study closure.

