#### **For the last chronological record for a condition/event**

- If outcome is “recovered/resolved”, “recovered/resolved with sequelae”, or “fatal” apply the following:
  - If only year is provided for the end date and year is equal to the year of the last dose date:
    - AE condition end date will be imputed as the minimum of (last dose date+30, death date, data extraction date, December 31st of the end date year)
  - If only year is provided for the end date and year is not equal to the year of the last dose date:
    - AE condition end date will be imputed as the minimum of (death date, data extraction date, December 31st of the end date year)
  - If month and year are provided for the end date:
    - AE condition end date will be imputed as the minimum of (death date, data extraction date, last day of the end date month/year)
- If outcome is “recovering/resolving”, “not recovered/resolved”, “unknown”, or blank:
  - AE condition end date will not be imputed.

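### SAP 7.6.1.1 summarises AESI time to resolution only among events that resolved, which understates duration for slow-resolving events, probably most for non-serious peripheral neuropathy

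*SAP*

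**What the plan says.** SAP 7.6.1.1 names three classes: "Adverse events of ocular AEs, peripheral neuropathy, and bleeding are considered AESI". It then defines two summaries.

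- **Time to resolution.** "Time to resolution will be summarized for events that meet certain search criteria and have the outcome of" recovered/resolved or recovered/resolved with sequelae. The clock runs from the start to the end of the event.
- **Time to improvement.** "For events that are not resolved, improvement is defined as a decrease by at least one grade from the worst grade", judged at the latest assessment. For these events, "time to improvement will be calculated as time from the worst grade of the event to the date the event is improved".

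Both are described by mean, standard deviation, median and range, and "Time to resolution and improvement will be summarized at the event level". No censoring, Kaplan-Meier or cumulative incidence estimate is mentioned. For the last record of an event that is recovering, not recovered, of unknown outcome or blank, SAP Appendix A says "AE condition end date will not be imputed". Such an event therefore has no duration. If it has not improved either, it enters neither summary. Sections 7.6.1 and 7.6.1.1 do not plan a count of AESI events resolved, improved or ongoing.

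Follow-up is set in Protocol 7.7.8.3. The general rule is "All non-serious AEs will be followed through the safety reporting period", a period that ends at the later of the end-of-treatment (EOT) visit and 30 days after the last dose. There are two exceptions. All ocular events are followed until they resolve or return to baseline, or until the study closes. Serious events are followed until they return to baseline, stabilise or lose clinical significance, or until death or withdrawal of consent.

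**The concern.** An event enters the time-to-resolution summary only if it ended while it was still being watched. The events left out are the longest ones, so the mean and median are pulled down. The pull grows with the share of events still open when follow-up stops. A reader who takes the planned median as the typical length of the toxicity would be misled, and nothing in the planned tables shows how many events are missing from it.

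The protocol's own background makes persistence a live question. Section 1.3.3.1 reports a Grade 3 conjunctivitis with irreversible damage on 0.9 mg/kg 3Q4W, the Part B regimen. It also calls peripheral neuropathy the leading cause of permanent discontinuation in the GEN701 cohort expansion. Once a patient stops for non-serious neuropathy, the period over which that event is followed soon ends.

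**Working it through.** The documents give no AESI duration or resolution share, so there is no planned figure to reproduce. The check has two parts.

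**1. Who is followed, and for how long**

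| Class | Follow-up (Protocol 7.7.8.3) | Expected bias |
|---|---|---|
| Non-serious neuropathy | Later of EOT visit and 30 days after last dose | Likely largest |
| Non-serious bleeding | Same | Near zero if events are brief; 1.3.3.1 describes mainly Grade 1 epistaxis but gives no duration |
| Ocular | To resolution, baseline or study closure | Smaller, not zero |
| Serious, any class | Beyond the reporting period | Smaller, not zero |

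Ocular and serious events can still be open at the primary data cut, because SAP 6.10 requires only the opportunity for 6 months of follow-up.

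**2. Size under stated assumptions**

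Assume exponential time to resolution with true median M, so λ = ln 2 / M. Assume follow-up from onset that is uniform between a and b weeks and independent of resolution. M, a and b are assumptions, not document figures.

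- Share resolved: p = 1 − (e^(−λa) − e^(−λb)) / (λ(b − a)).
- Resolved-only median, when it falls below a: m = −ln(1 − p/2) / λ. If it falls above a, m is solved numerically from the same distribution.

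For M = 12 weeks, λ = 0.0578:

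- Follow-up 4-20 weeks: p = 1 − (0.794 − 0.315)/0.924 = 0.48. The closed form gives a value just above a = 4, and the numerical solution is 4.8 weeks.
- Follow-up 12-52 weeks: p = 1 − (0.500 − 0.050)/2.310 = 0.805. Then m = −ln(1 − 0.4025)/0.0578 = 8.9 weeks.
- Follow-up 26-156 weeks: p = 1 − (0.2227 − 0.0001)/7.509 = 0.970. Then m = −ln(1 − 0.485)/0.0578 = 11.5 weeks.

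For M = 1 week and follow-up 4-20 weeks, p = 0.994 and m = 0.99 weeks.

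Varying M with follow-up held at 4-20 weeks:

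| True median (weeks) | Share resolved | Resolved-only median (weeks) |
|---|---|---|
| 4 | 83% | 3.1 |
| 8 | 62% | 4.3 |
| 12 | 48% | 4.8 |
| 16 | 39% | 5.1 |

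The true median quadruples while the resolved-only median moves by 2 weeks. With short follow-up, the planned statistic hardly separates a brief toxicity from a lasting one.

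Simulated Kaplan-Meier medians for these four rows, with open events censored, were 4.0, 8.0, 12.0 and about 16 weeks. That agreement depends on the simulated censoring being independent of resolution.

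**The case against.** The strongest reply is that the statistic is correct as labelled. The SAP says openly that it describes resolved events. It reports the number of observations (6.1), lists all treatment-emergent events (7.6.1) and gives shift tables. Duration is not among the safety endpoint's attributes (SAP 3.2), and no decision rule uses it. All of that stands, and it limits the weight of the point. It does not supply a resolved-versus-ongoing denominator, and a listing does not correct a median.

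A reader might infer three stronger things that the documents do not support.

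- **That a 12-week toxicity in any AESI class would be reported as about 5 weeks.** That figure needs follow-up of 4-20 weeks. Ocular events can be followed to study closure, which may be 3 years after the last enrolment (Protocol 3.1), and serious events also have extended follow-up. Even for non-serious neuropathy, an early event in a patient who stays on treatment is followed for a long time. Heavy truncation is plausible there but not shown.
- **That time to improvement also understates event duration.** It covers only unresolved events that improved and runs from the worst grade, so it does not measure duration. Applying it to all AESI events would redefine it.
- **That Kaplan-Meier would recover the truth.** Follow-up of non-serious events ends relative to the last dose, and these toxicities can themselves lead to discontinuation (Protocol 5.3), so censoring may be informative. Events also repeat within patients, and death competes with resolution. Censoring reduces the bias but need not remove it.

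**Conclusion.** The concern holds for time to resolution. The restriction to resolved events, with no censoring and no planned count of open events, understates duration where resolution is slow relative to follow-up. The direction follows from the definition. The size cannot be computed from the documents. For an assumed 12-week true median, the resolved-only figure ranges from about 4.8 to 11.5 weeks across the follow-up windows tried, and for a 1-week median there is almost no bias. These figures rest on exponential resolution and independent uniform follow-up.

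The ordering of the classes rests on the follow-up rules in Protocol 7.7.8.3 and on bleeding events being brief, which the documents suggest but do not state. This is a cheap improvement to a descriptive safety summary and has no bearing on the primary endpoint.

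**What to change.** In SAP 7.6.1.1:

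1. For each AESI class, over all events, report the number and percentage resolved, improved and ongoing at last follow-up.
2. Add a Kaplan-Meier estimate of time to resolution from onset, or a cumulative incidence estimate with death as a competing event. Censor open events at last AE follow-up, and name the date to be used, since these events have no end date.
3. State beside the estimate that censoring may be informative and that events repeat within patients.
4. Keep the current table, labelled 'resolved events only'.
5. Keep time to improvement as a separate summary, labelled 'unresolved events that improved, from worst grade', with the number of unresolved events as its denominator.

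The cost is SAP wording and one extra table from data already collected. Reported durations will look longer.
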